#### *Details of the Day 30 Follow-Up*

- Lost to Follow-up
- Whether subject entered one of the following programs:
  - None
  - Methadone
  - Buprenorphine
  - Naltrexone
  - Other
- Whether subject relapsed to drug use after exiting the study (Yes, No)

### **6.9 Safety analysis**

Safety measures will be summarized for the following:

- Safety Population
- Co-administered Buprenorphine;
- Co-administered Methadone
- Other (no co-administration of buprenorphine or methadone)
- and
- Any other identifiable co-administration categories not otherwise noted.

#### *Extent of exposure*

Extent of exposure will be described by whether the subject took the trial medication and the number of days' exposure (last date of medication minus first date of medication + 1). Average daily dose of study medication will also be calculated. No allowance will be made for breaks in therapy in the exposure calculations. If the date of last dosing is completely missing for the trial medication then the date of last dosing will be taken for analysis purposes as the date the medication was last dispensed. If only the month of the last dose is recorded, the first day of the month will be assumed as the last dosing date.

Additionally, the number and percentage of subjects with a dose reduction from 3.2 mg/day to 2.4 mg/day will be presented overall and for each co-administration category by study day.

palpitations	flushing, warm feeling	dizziness
presyncope	headache	pallor
	hypertension	shortness of breath
	hypertensive encephalopathy	
	lightheadedness	
syncope	nausea	
tachycardia	pallor	
	perspiration	
	shortness of breath	
	stroke/CVA	
	syncope	
	tachycardia	
	tremor	
	vision changes	

Narratives of deaths, serious and other significant AEs will be provided in the relevant section of the CSR.

A complete subject listing of all AEs will be provided in [Appendix 16.2](#) to the study report. This listing will include AE verbatim, MedDRA primary system organ class and preferred term, the time of onset and cessation of event relative to first dosing of study medication, duration of AE (for ongoing AEs use the date of investigator signature as the cessation date for calculation purposes), whether serious, severity, relationship to study medication, action taken and outcome.

Treatment emergent and non-treatment emergent events will be listed separately.

#### *Vital Signs Measurements*

Summary statistics for observed and changes from baseline in sitting and standing vital signs, separately, will be tabulated at each follow-up for each vital sign parameter and at post-baseline endpoint for each variable overall and for each co-administration category. All values will be included in the summary of potentially clinically significant vital signs. However, post-baseline repeat/unscheduled assessments will be excluded for the other tabulations.

In addition the number and proportion of subjects having PCS will be tabulated:

- Systolic blood pressure  $\geq 180$  mmHg and an increase of  $\geq 20$  mmHg from baseline
- Systolic blood pressure  $\leq 90$  mmHg and a decrease  $\geq 20$  mmHg from baseline;
- Diastolic blood pressure  $\geq 105$  mmHg and an increase  $\geq 15$  mmHg from baseline;

- Diastolic blood pressure  $\leq 50$  mmHg and a decrease  $\geq 15$  mmHg from baseline; or

Additionally, the number and proportion of subjects having a dose-hold due to a VS measurement will be tabulated as follows:

Resting (sitting [or recumbent if necessary because of an AE])

- Systolic blood pressure  $<90$  mmHg and  $>20\%$  below screen value;
- Diastolic blood pressure  $<50$  mmHg and  $>20\%$  below screen value;
- Pulse  $<50$  bpm and  $>20\%$  below screen value; or
- Symptoms of hypotension and/or bradycardia (e.g., lightheadedness, dizziness).

Orthostatic (after standing for 3 minutes)

- Systolic blood pressure diastolic blood pressure, or pulse  $>25\%$  below recumbent values.

In addition, the number and proportion of subjects meeting the discontinuation Vital Signs criteria will be tabulated as follows:

- Resting systolic blood pressure  $<70$  mmHg;
- Resting diastolic blood pressure  $<40$  mmHg;
- Resting pulse  $<40$  bpm;
- QTcF  $>500$  msec or  $>25\%$  above screen value for both males and females; or
- Syncope.
- Persistent symptomatic hypotension (e.g., hypotension not responding to bed rest or fluids).
- Single occurrence of symptomatic bradycardia (as assessed by Principal Investigator/study physician/assigned staff, regardless of blood pressure) associated with chest pain, shortness of breath, or decreased level of consciousness.
- Persistent hypertension – resting blood pressure  $\geq 185/110$  mmHg recorded on 3 separate occasions taken at least 5 minutes apart AND within a 1-hour time period. If 2 of 3 readings are  $\geq 185/110$  mmHg (either systolic  $\geq 185$  mmHg or diastolic  $\geq 110$  mmHg) the subject must be discontinued.

All of the above will be summarized overall and for each co-administration category at each study day.

The incidence of missed standing vital signs will be counted for those subjects with a resting blood pressure measurement and a missing standing blood pressure measurement. The count of unique subjects and number of events will be tabulated. Consecutive missing measurements will be counted as one event. Additionally, the number of missed doses and the reason for each missed dose will be presented for each subject and study day.

The number and percentage of subjects with a reduced dose that still met each of the above criterion after the dose reduction will be presented overall and for each co-administration category by study day.

Mean profiles by study day will be presented for sitting and standing blood pressure and pulse rate.

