## **10.4 Dose Hold and Discontinuation Criteria (2 of 3 Rule)**

When a blood pressure, heart rate, or QTcF interval value meets criteria for withholding a dose (Section 13.2.2) or discontinuation from the study (Section 13.2.3), the value needs to be confirmed by the site personnel by repeating the vital sign measurement or ECG recording, approximately 10 to 15 minutes later. If the value is confirmed by the second measurement, the appropriate action will be taken (dose hold or study discontinuation) and the confirmatory value will be recorded in the subject's source document and appropriate eCRF. If the second value does not meet the specified criteria, a third measurement will be taken approximately 10 to 15 minutes later. If this value is confirmatory, the appropriate action will be taken (dose hold or study discontinuation) and the last confirmatory value will be recorded in the subject's source document and appropriate eCRF. If the third value does not confirm the initial finding, then no action should be taken and the third value should be entered in the subject's source and appropriate eCRF. Note that should a second or third measurement be required with waiting between measurements, the timing of the

measurement will not be considered a protocol deviation (i.e., outside the protocol-specified window).

Whenever blood pressure, heart rate, or QTcF interval values meet dose hold or study discontinuation criteria, these are to be recorded on the subject's eCRF as an adverse event (AE) or serious adverse event (SAE), as applicable. Examples are:

Item	Record Adverse Event of:
Resting Vital Signs	
SBP <90 mmHg and >20% below screen value	Hypotension
DBP <50 mmHg and >20% below screen value	Hypotension
Pulse <50 bpm and >20% below screen value	Bradycardia
Orthostatic Vital Signs	
SBP >25% below recumbent values	Postural hypotension
DBP <25% below recumbent values	Postural hypotension
Pulse >25% below recumbent values	Postural bradycardia

DBP = diastolic blood pressure, SBP = systolic blood pressure

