#### **Section 6.10 Vital Signs Measurements**

Change: Addition of the incidence of missing standing vital signs measurements.

Reason: There is interest in determining the number of subjects who could not stand.

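### SAP 6.9 derives no standing-minus-resting change, so the size of postural falls and the measured share above 25% at 3.5 hours post-dose go unreported; protocol 10.4 also misprints its diastolic example

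*SAP*

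**What the plan says.** Safety is the primary objective. The protocol synopsis lists orthostatic hypotension and orthostatic bradycardia, with syncope, as AEs of special interest. Protocol 15.5.2 pairs a reading after 3 minutes at rest with one after 3 minutes standing, if the subject is able to stand. In clinic this is done before all four daily doses and 3.5 hours after three of them. Section 15.3.1 treats 3.5 hours as the estimated time of peak concentration.

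SAP 6.9 (Vital Signs Measurements) then states: "Summary statistics for observed and changes from baseline in sitting and standing vital signs, separately, will be tabulated at each follow-up". The figures follow the same split: "Mean profiles by study day will be presented for sitting and standing blood pressure and pulse rate". The four PCS rules combine a blood pressure level with a change from baseline. On which readings count, the SAP says "All values will be included in the summary of potentially clinically significant vital signs", and then "However, post-baseline repeat/unscheduled assessments will be excluded for the other tabulations". Neither these rules nor the discontinuation criteria compare the two positions.

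The one rule that does, a fall of more than 25%, appears in the dose-hold table. It applies again by reference in a table of "The number and percentage of subjects with a reduced dose that still met each of the above criterion after the dose reduction". SAP 6.10 adds a count of missing standing readings, because "There is interest in determining the number of subjects who could not stand".

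Protocol 13.2.2 bases holds on pre-dose readings and sets the postural threshold at more than 25% for systolic pressure, diastolic pressure and pulse. The AE examples in protocol 10.4 agree for systolic pressure and pulse, but the diastolic row reads "DBP <25% below recumbent values".

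**The concern.** A postural fall belongs to a pair of readings. Summaries of each position alone give the mean fall by subtraction, exactly so if every pair is complete. They say nothing about how falls vary between subjects. The safety question is about the tail: how many subjects drop sharply on standing, by how much, and whether this happens around peak concentration.

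Without a paired summary, the study would report a count of postural AEs with no measured figure to set beside it. Those AEs are recorded by sites, and the table that illustrates how to record them has its diastolic row the wrong way round.

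**Working it through.** **1. Schedule.** In clinic, 4 pre-dose + 3 post-dose sets = 7 per day, which reproduces the figure in protocol 15.3.1. Days 1-3 give 3 x 7 = 21 pairs: 12 pre-dose and 9 post-dose (9/21 = 43%). Outpatient days have 1 pre-dose and 1 post-dose set, except Day 14, which has 1 pre-dose only. Excluding the end-of-study visit:

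| Course | All pairs | Post-dose pairs |
|---|---|---|
| In clinic Days 1-7 | 7 x 7 = 49 | 7 x 3 = 21 (43%) |
| In clinic Days 1-3, outpatient Days 4-7 | 21 + 8 = 29 | 9 + 4 = 13 (45%) |
| In clinic Days 1-3, outpatient Days 4-14 | 21 + 20 + 1 = 42 | 9 + 10 = 19 (45%) |

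The outpatient rows are upper limits. A 3.5-hour reading may be taken at home, and the diary form is not shown, so it is unknown whether both positions are recorded there. In clinic, every post-dose pair is followed by a hold-eligible pre-dose pair, nominally 1 to 1.5 hours later. The permitted windows stretch that to about 0 to 2.5 hours. Outpatient post-dose pairs (4 of 13, or 10 of 19) have no such follow-up until the next daily visit.

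**2. Where a fall above 25% appears in the results.**
- *Pre-dose, confirmed:* 13.2.2 requires a hold. SAP 6.3 puts every output except disposition on the Safety Population, so the dose-hold table gives a share of all treated subjects.
- *Post-dose:* 10.4 and 15.5.2 require an AE, which reaches the treatment-emergent AE tables. Some blood pressure falls also meet a PCS rule.
- *Reduced-dose subjects:* the criteria are tabulated again, for that subset only.

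**3. What separate summaries cannot show.** Take three subjects resting at 150, 130 and 110 (invented values).
- A: standing 140, 120, 100. Falls 6.7%, 7.7%, 9.1%; mean fall 10, SD of falls 0; 0 of 3 above 25%.
- B: standing 100, 140, 120. Falls 33.3%, -7.7%, -9.1%; mean fall 10, SD of falls 34.6; 1 of 3 above 25%.

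Standing mean (120), SD (20), quartiles and range are the same in both. With a common standing baseline of, say, 130, the changes from baseline also match: +10, -10, -30 in A and -30, +10, -10 in B.

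The same point with a bivariate normal model and assumed systolic values, resting R 115 (SD 13) and standing S 105 (SD 15):
- mean of S - 0.75R = 105 - 86.25 = 18.75
- variance = 15² + 0.5625 x 13² - 1.5 x ρ x 13 x 15
- P(S < 0.75R) = 10.9%, 7.7%, 4.0% and 0.6% at ρ = 0.3, 0.5, 0.7 and 0.9

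The separate means and SDs never change.

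**4. PCS as a substitute.** From resting value r, reaching the low PCS level needs a fall of (r - 90)/r systolic or (r - 50)/r diastolic.
- Systolic: 25% at 120, 33% at 135, 42% at 155.
- Diastolic: 25% at 66.7, 37.5% at 80, 47% at 95.
- 118 to 86 (27%) with standing baseline 112 is counted, since 112 - 86 = 26 is at least 20.
- 135 to 100 (25.9%) is not counted, since 100 is above 90.
- 92 to 88 (4%) with baseline 115 is counted, although it is hardly postural.

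**5. Incomplete pairs.** Suppose subjects able to stand go from 120 to 110 and those unable rest at 90 (assumption). With 2%, 5% or 10% unable, the resting mean is 119.4, 118.5 or 117.0. The difference of means is then 9.4, 8.5 or 7.0 instead of 10.

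**6. Diastolic example.** Read literally, 80 to 76 (5%) is postural hypotension and 80 to 56 (30%) is not. Section 13.2.2 gives the opposite in both cases. The Amendment 01 text prints the same sign, so a misread of the PDF is unlikely.

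**The case against.** The strongest reply is that the plan already counts threshold crossings. Pre-dose, every confirmed fall above 25% must become a hold and is tabulated over the Safety Population. Post-dose, recording an AE is triggered by the reading itself, and SAP Table 2 includes orthostatic hypotension. The protocol's endpoints are AE occurrence and descriptive vital signs; no paired endpoint is promised, and SAP 6.1 allows further tables.

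Most of this stands. A reader might infer that ordinary subjects' postural falls are invisible because the threshold sits in the dose-hold table. The documents do not support that: the hold defines the numerator, not the population. A reader might also infer that post-dose falls go unreported, and 10.4 and 15.5.2 say otherwise.

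What the reply leaves open is the size and spread of falls, the pre-dose versus post-dose split, and any check that sites turned qualifying readings into AEs.

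Two gaps in the public copy also limit the point. The SAP's table and figure lists are blank, so an unlisted output cannot be excluded. The printed PCS list has no pulse rule but ends on a dangling conjunction, so nothing is built on that absence.

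**Conclusion.** The point holds in limited form. As written, SAP 6.9 yields a proportion with pre-dose holds, AE counts and an approximate mean fall. It does not yield the distribution of falls, or the measured share of subjects falling more than 25% at 3.5 hours post-dose. It also offers no way to check the AE counts against the readings. About 43% of in-clinic pairs are post-dose; the outpatient figures depend on what the diary records. The illustrations in steps 3 and 5 use assumed values. They show that separate summaries cannot determine the rate, not what the rate is in this trial.

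The diastolic row in 10.4 is wrong against its neighbouring rows and 13.2.2. A reader might infer that diastolic AEs were misrecorded. The documents do not show that: the row sits among examples, the text above it points to the dose-hold criteria, and those are correct. This should be fixed in a safety study, but it does not undermine the planned results.

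**What to change.** In SAP 6.9:
- Derive standing minus the paired resting value, absolute and percent, for systolic pressure, diastolic pressure and pulse.
- Summarise by study day and co-administration category, separately for pre-dose and 3.5 hours post-dose. Flag home readings where both positions were recorded.
- Report the number and percentage of subjects with any paired fall above 25%, among those with at least one complete pair, beside the postural AE and missed-standing counts.
- Use the reading that protocol 10.4 sends to the eCRF: the confirming repeat or, if unconfirmed, the third reading ("If the third value does not confirm the initial finding, then no action should be taken and the third value should be entered"). Pair it with the resting value of the same attempt. State that it is not dropped under the SAP's exclusion of repeats.
- Define the comparator as the paired resting value, sitting or recumbent. The threshold text says recumbent, whereas 15.5.2 has subjects sitting unless an AE prevents it.

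In protocol 10.4, change the diastolic example to more than 25%.

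The SAP part costs one derived variable and one table, with no new procedures. Check first whether the diary holds both positions. The protocol part corrects one sign in an examples table and leaves the hold rule in 13.2.2 unchanged.

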### 13.2.2 Dose Hold Criteria

Study medication will be held if pre-dose vital signs meet any of the criteria listed below (see Section 10.4 for details on repeat confirmatory requirements).

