### 13.2.3 Discontinuation Criteria

A subject will be discontinued from the study if any of the criteria listed below are met (see Section 10.4 for details on repeat confirmatory requirements). All instances should be recorded in the subject's source document and AE or SAE eCRF, as applicable.

- Resting systolic blood pressure <70 mmHg;
- Resting diastolic blood pressure <40 mmHg;
- Resting pulse <40 bpm;
- QTcF >500 msec or >25% above screen value for both males and females; or
- Syncope.

Additional discontinuation criteria based on cardiovascular events are:

- New onset of clinically significant abnormal ECG per Investigator judgment (e.g., second or third degree heart block or uncontrolled arrhythmia, prolonged QTcF interval).
- Persistent symptomatic hypotension (e.g., hypotension not responding to bed rest or fluids).
- Single occurrence of symptomatic bradycardia (as assessed by Principal Investigator/study physician/assigned staff, regardless of blood pressure) associated with chest pain, shortness of breath, or decreased level of consciousness.
- Persistent hypertension – resting blood pressure  $\geq 185/110$  mmHg recorded on 3 separate occasions taken at least 5 minutes apart AND within a 1-hour time period. If 2 of 3 readings are  $\geq 185/110$  mmHg (either systolic  $\geq 185$  mmHg or diastolic  $\geq 110$  mmHg) the subject must be discontinued.
- Medical Intervention for Cardiovascular Event: Any medical intervention (nonmedication or medication inclusive) used for the treatment of any cardiovascular event, with the exception of a positional intervention in subjects displaying hypotension.
- Any other clinically significant cardiovascular signs or symptoms that would place the subject at risk.
- Subject misses more than a total of 6 doses during Days 1-7.

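### The SAP's list of potentially clinically significant vital signs has no pulse criterion, so a post-dose pulse of 40–49 bpm, judged on its value alone, is not counted in the PCS, dose-hold or discontinuation table

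*SAP*

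**What the plan says.** SAP 6.9, Vital Signs Measurements, plans three threshold tables on the whole Safety Population and one on a subset.

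- **PCS table.** "In addition the number and proportion of subjects having PCS will be tabulated". The four criteria are high systolic, low systolic, high diastolic and low diastolic pressure, each paired with a change from baseline. The fourth ends "mmHg from baseline; or", and the next line begins the dose-hold table. On coverage the SAP says: "All values will be included in the summary of potentially clinically significant vital signs". Post-baseline repeat and unscheduled readings are left out of the other tabulations.
- **Dose-hold table.** Here "the number and proportion of subjects having a dose-hold due to a VS measurement will be tabulated as follows". Its rows repeat the protocol's hold criteria, including "Pulse <50 bpm and >20% below screen value" and an orthostatic pulse criterion.
- **Discontinuation table.** Its pulse row is "Resting pulse <40 bpm". A separate row covers symptomatic bradycardia with chest pain, shortness of breath or reduced consciousness, without a pulse cut-off.
- **Dose-reduced subjects.** A later paragraph counts subjects on a reduced dose who still met any of the preceding criteria after the reduction.

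Protocol 13.2.2 fixes the timing of holds: "Study medication will be held if pre-dose vital signs meet any of the criteria listed below". Protocol 15.5.2 treats values meeting 13.2.2 or 13.2.3 as potentially clinically significant at either time, before or after a dose, and requires an adverse event record. SAP 6.10, which declares departures from the protocol's analysis, does not mention dropping pulse from the PCS definition.

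**The concern.** The trailing *or* suggests that a fifth criterion was intended, and pulse is the obvious candidate: the protocol's own definition includes it, and the PCS table is the only one stated to use every value.

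Safety is the primary objective. The protocol treats slow pulse as a principal risk: it excludes a screening pulse below 55 bpm, excludes beta-blockers to avoid excessive bradycardia, and names orthostatic bradycardia as an event of special interest. The 3.5-hour readings are timed to the estimated peak concentration (protocol 15.3.1), where a pulse effect is most likely to show.

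A count of subjects from measured values is the independent check on adverse event reporting. Blood pressure has that check; pulse after dosing does not. The check matters most for outpatient readings, where the 3.5-hour value may be self-measured and written in a diary.

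**Working it through.** The plan gives no figure to reproduce. The check is whether a post-dose resting pulse of 40–49 bpm satisfies a row of each table.

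**Inputs**
- Lowest screening pulse allowed: 55 bpm (protocol 11.2.2).
- Hold criterion for pulse: below 50 bpm and more than 20% below screening (protocol 13.2.2, repeated in SAP 6.9).
- Discontinuation criterion for pulse: below 40 bpm (protocol 13.2.3, repeated in SAP 6.9).
- In-clinic readings: before each of 4 doses and 3.5 hours after 3 of them (protocol 15.3.1), so 4 + 3 = 7 a day, of which 3 are post-dose.
- Assumption: screening pulse from 55 to 100 bpm. The protocol sets no upper limit.

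**Grid.** Integer screening pulses 55 to 100 give 46 values. Integer post-dose pulses 40 to 49 give 10. Together, 46 × 10 = 460 pairs.

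| Table | Test applied to a post-dose reading | Pairs counted |
|---|---|---|
| PCS | no pulse row | 0 of 460 |
| Discontinuation | pulse < 40 | 0 of 460 |
| Dose-hold, counting holds | a hold requires a pre-dose reading | 0 of 460 |
| Dose-hold, if programmed as any reading meeting the criterion | pulse < 50 and pulse < 0.8 × screening | 437 of 460 |

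These are grid counts, not expected frequencies.

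**The 23 pairs that the protocol threshold leaves out.** A reading fails the criterion when it is at or above 0.8 × screening. At a screening pulse of 55 the limit is 0.8 × 55 = 44, so 44–49 fail (6 values). Screening pulses of 56, 57, 58, 59, 60 and 61 leave out 5, 4, 3, 2, 2 and 1. The sum is 6 + 5 + 4 + 3 + 2 + 2 + 1 = 23, and 460 − 23 = 437. From 62 bpm upward every value of 40–49 qualifies, since 49 / 0.8 = 61.25. The 23 therefore do not depend on the assumed upper limit of 100.

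**Other places where these readings appear**
- *Descriptive statistics.* Observed and change values for each vital sign at each follow-up, with minimum and 25th percentile (SAP 5.1 and 6.9), plus mean profiles. A minimum shows whether any scheduled reading fell below 50, but not in how many subjects, and not relative to each subject's screening value.
- *Adverse events.* Values meeting 13.2.2, pre- or post-dose, must be recorded (protocol 10.4 and 15.5.2) and reach the treatment-emergent event tables.
- *Next pre-dose reading.* In clinic, nominal post-dose times are 11:30 AM, 4:30 PM and 9:30 PM. Pre-dose readings fall within 30 minutes before 1, 6 and 11 PM, so 60 to 90 minutes later. Bradycardia that persists and causes a hold is counted there.
- *Dose-reduced subjects.* That table is worded as meeting a criterion and states no pre-dose limit, so qualifying post-dose readings in this subset may be counted.

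**The case against.** The strongest answer is that little is lost. Adverse event entry is mandatory at a fixed numeric threshold with a confirmation rule; pulse has full descriptive statistics; persistent bradycardia can reach the hold table; symptomatic bradycardia with the listed features has its own row; and ventricular rate is computed from ECGs after the first dose and around the last dose, under a separate plan. The protocol's vital-sign endpoint is descriptive, and its section 17.3 promises no PCS table. All of that stands. A reader might infer that post-dose bradycardia goes untabulated, or that its incidence rests only on whether sites remember to report it. The documents support neither reading.

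Nor do they support saying that no vital-sign threshold table could ever count such a reading. The dose-reduced table may count some. The pre-dose limit on the hold table comes from the protocol rather than the SAP, so a programmer could apply the row to all readings. That is an ambiguity to settle, although the SAP's words refer to subjects having a hold.

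It can also be said that the missing item was lost when the PDF was read, or that a pulse table is listed in SAP section 7, of which the public copy shows only column headings. Neither can be excluded, but the text around the list shows no gap or redaction mark.

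Finally, the protocol threshold would not capture every reading of 40–49 bpm, and it places a percentage rule in a list built on absolute changes. Both observations are correct. They bear on the choice of row, not on whether one is needed.

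**Conclusion.** The point holds as a gap in threshold counts. The SAP's PCS list is incomplete on its face and narrower than protocol 15.5.2, without a declared change. Followed as written, the PCS, dose-hold and discontinuation tables give no subject count for a post-dose pulse of 40–49 bpm judged on value alone: 0 of 460 grid pairs. In clinic this concerns 3 of 7 daily readings. It does not follow that 3 of 7 episodes are missed, because an episode may persist to the next pre-dose reading. The number of subjects affected cannot be estimated, since the documents give no rate.

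The conclusion rests on two readings: that the dose-hold table counts holds, as worded, and that holds follow pre-dose values, as in protocol 13.2.2. If the dose-hold table were instead programmed on all readings, 437 of 460 pairs would be counted and the remaining defect would be the unfinished PCS list. The events themselves are not lost to the study on either reading.

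**What to change.** 1. Complete the PCS list in SAP 6.9 with a pulse row applied to all pre- and post-dose values. Either restore the sponsor's dropped criterion or use the existing threshold of protocol 13.2.2 purely as a reporting rule. The hold and discontinuation rules are untouched.
2. Reconcile the list with protocol 15.5.2, or declare the difference in SAP 6.10.
3. State whether the dose-hold table counts subjects with a hold or subjects with any reading meeting the criterion, and apply the same statement to the table of dose-reduced subjects.
4. If the 13.2.2 threshold is used, note that some readings of 44–49 bpm stay uncounted when screening pulse is 55–61 bpm.

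A matching row for standing against resting pulse is optional.

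The cost is one row in a planned table and a sentence or two of text. SAP 6.2 already sets the last screening measurement as the vital-sign baseline, so the reference value exists and no new data are needed.
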